### **3 STUDY OBJECTIVES**

#### **3.1 PRIMARY OBJECTIVE**

- To evaluate the efficacy of pamiparib in patients with positive mCRPC for circulating tumor cells with homologous recombination deficiency (CTC-HRD-positive; per Epic Sciences assay), as per PCWG3 criteria

[figure not shown]
#### **3.2 SECONDARY OBJECTIVES**

- To further evaluate the efficacy of pamiparib in patients with CTC-HRD-positive mCRPC with measurable disease (Cohort 1 of Table 1), as per PCWG3 criteria
- To further evaluate the efficacy of pamiparib in patients with CTC-HRD-positive mCRPC with or without measurable disease (Cohorts 1 and 2 of Table 1, respectively), as

[figure not shown]
per PCWG3 criteria

- To evaluate the safety and tolerability of pamiparib

### 3.3 EXPLORATORY OBJECTIVES

- 
- 
- 
- 

## 4 STUDY ENDPOINTS

### 4.1 PRIMARY ENDPOINTS

- Objective response rate (ORR; defined as the proportion of patients with best objective response of complete response (CR) or partial response (PR) confirmed at a subsequent timepoint  $\geq 4$  weeks later) by Independent Review Committee (IRC) for CTC-HRD-positive patients with measurable disease (Cohort 1 of Table 1)
- PSA response rate (defined as the proportion of patients with PSA decline  $\geq 50\%$  from baseline [confirmed by a second PSA value  $\geq 3$  weeks later]) for CTC-HRD-positive patients with or without measurable disease (Cohorts 1 and 2 of Table 1, respectively)

### 4.2 SECONDARY ENDPOINTS

For Patients with CTC-HRD-Positive mCRPC with Measurable Disease (Cohort 1 of Table 1) per PCWG3 Criteria:

- Duration of response (DOR) by IRC
- ORR by investigator
- Time to objective response
- Clinical benefit rate (defined as the proportion of patients with a documented confirmed CR, PR, or stable disease)

For Patients with CTC-HRD-Positive mCRPC with or without Measurable Disease (Cohorts 1 and 2 of Table 1, respectively) per PCWG3 Criteria:

- Time to PSA response

- Duration of PSA response
- Time to PSA progression (defined as the time from the date of the first dose of study drug to a  $\geq 25\%$  increase in PSA with an absolute increase of  $\geq 2$  ng/mL above the nadir [or above the baseline for patients with no PSA decline] after 12 weeks, confirmed by a second value  $\geq 3$  weeks later)
- Time to symptomatic skeletal event (SSE; defined as time from the date of the first dose of study drug to the first symptomatic fracture, radiation or surgery to bone, or spinal cord compression)
- Radiographic progression-free survival (rPFS; defined as the time from the date of the first dose of study drug to radiographic disease progression by IRC or death due to any cause, whichever occurs first)
- Overall survival (OS)

For All Patients (Cohorts 1, 2, 3, and 4 of [Table 1](#)):

- Incidence, timing, and severity of treatment-emergent adverse events (TEAEs), graded according to NCI-CTCAE Version 4.03 or higher

#### 4.3 EXPLORATORY ENDPOINTS

- 
- 
- 
- 
- 
- 

## 5 SAMPLE SIZE CONSIDERATIONS

This study is designed to provide adequate power for primary endpoints of ORR and PSA response rate. A sample size of approximately 100 patients is planned (at approximately 45 centers with a projected average enrollment of 2 to 3 patients per center).

Assuming ORR of 35% for pamiparib in CTC-HRD-positive patients versus 15% for historical control in patients with measurable disease, the study power is 88% using a binominal exact test and 1-sided type-I error of 0.025 with  $n = 50$ . The binominal exact 95% CI of 35% ORR is 22.1% to 49.8% with a sample size of 50 patients.

Assuming PSA response rate of 50% for pamiparib versus 30% for historical control in CTC-HRD-positive patients with or without measurable disease, a sample size of 80 patients in this population will provide 95% study power using a binominal exact test and 1-sided type-I error of 0.025. The binominal exact 95% CI of 50% response rate is 38.6% to 61.4% with  $n = 80$ .

To explore the efficacy of pamiparib in patients with CTC-HRD-negative, but BRCA1/2-mutant mCRPC with or without measurable disease, approximately 20 patients will be enrolled in these cohorts.

## 6 STATISTICAL METHODS

### 6.1 ANALYSIS POPULATIONS

- Safety Analysis Set (SAF): includes all patients enrolled in the study who receive any dose of pamiparib. The Safety Analysis Set will be used for all safety analyses.
- Efficacy-Evaluable Analysis Set (ORR Assessment in Cohort 1 of Table 1): includes all patients in the Safety Analysis Set who had measurable disease at baseline and at least 1 postbaseline tumor assessment, unless they permanently discontinue pamiparib or the study early due to clinical progression or death prior to tumor assessment. A similar analysis population will exist for exploratory analyses of Cohort 3.
- Efficacy-Evaluable Analysis Set (PSA Response Rate Assessment in Cohorts 1 and 2 of Table 1): includes all patients in the Safety Analysis Set as per Inclusion Criterion 7 at baseline ( $\geq 3$  rising PSA levels with  $\geq 1$  week between determinations and screening PSA  $\geq 2$   $\mu\text{g/L}$ ) and who had at least 1 postbaseline PSA measurement, unless they permanently discontinue pamiparib or the study early due to clinical progression or death before completed PSA assessment. A similar analysis population will exist for exploratory analyses of Cohorts 3 and 4.
- PK Analysis Set: includes all patients who received pamiparib and contributed at least one plasma concentration.

### 6.2 DATA ANALYSIS GENERAL CONSIDERATIONS

#### 6.2.1 Definitions and Computations

Study day: Study day will be calculated in reference to the date of the first dose of study treatment. For assessments conducted on or after the date of the first dose of study treatment, study day will be calculated as (assessment date – date of first dose of study treatment + 1). For assessments conducted before the date of the first dose of study treatment, study day is calculated as (assessment date – date of first dose of study treatment). There is no study day 0.

In the situation where the event date is partial or missing, the date will appear partial or missing in the listings. Study day and any corresponding durations will be presented based on the imputations specified in Appendix **Error! Reference source not found.**

Treatment duration: The treatment duration will be calculated as (date of last dose of study treatment – date of first dose of study treatment + 1).

Baseline: Unless otherwise specified, a baseline value is defined as the last non-missing value collected on or before the first dose date.

All calculations and analyses will be conducted using SAS version 9.2 or higher.

### 6.2.2 Conventions

Unless otherwise specified, the following conventions will be applied to all analyses:

- 1 year = 365.25 days. Number of years is calculated as (days/365.25) rounded up to 1 decimal place.
- 1 month = 30.4375 days. Number of months is calculated as (days/30.4375) rounded up to 1 decimal place.
- P-values will be rounded to 4 decimal places. P-values that round to 0.0000 will be presented as '< 0.0001' and p-values that round to 1.000 will be presented as '> 0.9999'.
- Duration of imaging-based event endpoints (such as PFS) will be based on the actual date the radiograph was obtained rather than the associated visit date.
- Missing efficacy or safety data will not be imputed unless otherwise specified.
- For laboratory results collected as < or >, a numeric value, 0.0000000001 will be subtracted or added, respectively, to the value.
- For by-visit observed data analyses, percentages will be calculated based on the number of patients with nonmissing data as the denominator, unless otherwise specified.
- For continuous endpoints, summary statistics will include n, mean, standard deviation, median, Q1, Q3 and range (minimum and maximum).
- For discrete endpoints, summary statistics will include frequencies and percentages.

### 6.2.3 Handling of Missing Data

Missing data will not be imputed unless otherwise specified elsewhere in the SAP. Missing dates or partially missing dates will be imputed conservatively for adverse events and prior/concomitant medications/procedures. Specific rules for handling of missing or partially missing dates for adverse events and prior/concomitant medications/procedures are provided in Appendix 10.1.

By-visit endpoints will be analyzed using observed data, unless otherwise specified. For observed data analyses, missing data will not be imputed and only the observed records will be included.

When summarizing categorical variables, patients with missing data are included in the denominator to calculate percentages unless otherwise specified. When needed, the category of “Missing” is created and the number of patients with missing data is presented.

When summarizing continuous variables, patients with missing data are not included in calculations. No imputations are made.

For the Health-related quality of life (HRQoL) questionnaires, the missing data will be handled in accordance with the scoring manual of each patient-reported outcome (PRO) questionnaire (Cleeland, 2009).

#### **6.2.4 Multiplicity Adjustment**

To control the overall study type I error rate, the primary efficacy endpoint analyses for ORR and PSA response rate will be tested sequentially.

If the hypothesis test for ORR is statistically significant at a one-sided 0.025 level (ie, one-sided  $p\text{-value} < 0.025$ ), then the PSA response rate will be tested at a one-sided 0.025 significance level. If the primary endpoint of ORR is not statistically significant, the primary endpoint of PSA response rate will not be tested for statistical significance.

### **6.3 PATIENT CHARACTERISTICS**

#### **6.3.1 Patient Disposition**

The following patient disposition information will be summarized:

- Number of patients treated
- Number (%) of treated patients who discontinued from treatment
- Reason(s) for treatment discontinuation
- Number (%) of treated patients who remain on treatment
- Number (%) of treated patients who discontinued from study
- Reason(s) for study discontinuation
- Number (%) of treated patients who remain in study
- Treatment follow-up time: defined as the time from the first dose date to the end of treatment date for patients discontinued from the treatment, or the database cutoff date for ongoing patients.

- Study follow-up time: defined as the time from the first dose date to death date or end of study date (whichever occurred first) for patients who discontinued study or the data cutoff date for ongoing patients.

### **6.3.2 Protocol Deviations**

Major protocol deviation criteria will be established and patients with major protocol deviations will be identified and documented before the database lock. Major protocol deviations will be presented for the Safety Analysis Set in a listing.

### **6.3.3 Demographics and Other Baseline Characteristics**

Demographics and baseline characteristics including following variables will be summarized using descriptive statistics:

- Race
- Age (years) and age group (years) as  $< 65$ ,  $\geq 65$
- Ethnicity
- Eastern Cooperative Oncology Group (ECOG) performance status at screening
- Time from initial diagnosis to study entry (Year)
- Metastases (Liver or lung)
- Baseline PSA
- Baseline hemoglobin
- Baseline LDH
- Baseline ALP

### **6.3.4 Prior Anti-Cancer Systemic Therapies**

The number of prior line of anti-cancer therapies and number of prior regimens will be summarized by cohort and overall for the Safety Analysis Set. The therapies with the same sequence/regimen number are counted as one prior therapy.

### **6.3.5 Prior and Concomitant Medications**

Prior and concomitant medications will be coded using the version of World Health Organization Drug Dictionary (WHO DD) drug codes and will be further classified to the appropriate Anatomical Therapeutic Chemical (ATC) code.

The number and percentage of patients reporting prior and concomitant medications will be summarized by ATC medication class and WHO DD preferred term for the Safety Analysis Set by cohort and overall. Prior medications are defined as medications that started and ended before the first dose date. Concomitant medications are defined as medications that (1) started before the first dose of study treatment and were continuing at the time of the first dose of study treatment, or (2) started on or after the date of the first dose of study treatment up to 30 days after

the patient's last dose or initiation of a new anti-cancer therapy. A listing of prior and concomitant medications will be provided.

### 6.3.6 Medical History

Medical History will be coded using MedDRA (version 20.0 or higher). The number and percentage of patients reporting a history of any medical condition, as recorded on the electronic case report form (eCRF), will be summarized by system organ class (SOC) and preferred term (PT) for the Safety Analysis Set by cohort and overall. A listing of medical history will be provided.

## 6.4 EFFICACY ANALYSIS

Table 2 summarizes the primary and secondary efficacy endpoints and corresponding analysis populations. If applicable, the specific cohort(s) or evaluable population being analyzed for each efficacy analysis will be specified.

**Table 2 Primary and Secondary Efficacy Endpoint Analysis Populations**

	Efficacy Endpoint	Analysis Population
Primary	ORR by IRC	Efficacy-Evaluable Analysis Set (ORR Assessment in Cohort 1)
	PSA Response	Efficacy-Evaluable Analysis Set (PSA Response Rate Assessment in Cohorts 1 and 2)
Secondary	DOR by IRC	Efficacy-Evaluable Analysis Set (ORR Assessment in Cohort 1), those w/objective response per IRC
	ORR by INV	Efficacy-Evaluable Analysis Set (ORR Assessment in Cohort 1)
	Time to Objective Response by INV	Efficacy-Evaluable Analysis Set (ORR Assessment in Cohort 1), those w/confirmed objective response per INV
	Clinical Benefit Rate by INV	Efficacy-Evaluable Analysis Set (ORR Assessment in Cohort 1)
	Time to PSA Response	Efficacy-Evaluable Analysis Set (PSA Response Rate Assessment in Cohorts 1 and 2), those w/confirmed PSA response
	Duration of PSA Response	Efficacy-Evaluable Analysis Set (PSA Response Rate Assessment in Cohorts 1 and 2), those w/confirmed PSA response
	Time to PSA Progression	Safety Analysis Set (Cohorts 1 and 2)
	Time to SSE	Safety Analysis Set (Cohorts 1 and 2)
	rPFS by IRC	Safety Analysis Set (Cohorts 1 and 2)
OS	Safety Analysis Set (Cohorts 1 and 2)	

Abbreviations: DOR = duration of response; INV = investigator; IRC = independent review committee; ORR = objective response rate; OS = overall survival; PSA = prostate-specific antigen; rPFS = radiographic progression-free survival; SSE = symptomatic skeletal event.

### 6.4.1 Primary Efficacy Endpoints

#### Objective Response Rate (ORR) by IRC

ORR is defined as the proportion of patients with a best objective response of CR or PR confirmed at a subsequent timepoint  $\geq 4$  weeks later. For this primary efficacy endpoint, the tumor assessments will be performed by the IRC and will be summarized for the Efficacy-Evaluable Analysis Set (ORR Assessment in Cohort 1).

ORR (number and proportion of patients) will be presented along with its Clopper-Pearson 2-sided 95% confidence interval. The number and proportion of patients who achieve an unconfirmed best objective response of CR or PR will also be summarized.

ORR will be tested against a historical control ORR, and the null and alternative hypotheses are as follows:

$$H_0: \text{ORR} = 15\%$$

$$H_a: \text{ORR} > 15\%$$

A binomial exact test will be performed for the above hypotheses at a one-sided 0.025 significance level. If the result for ORR is statistically significant, ie, one-sided p-value  $< 0.025$ , then the primary efficacy endpoint of PSA response rate will be tested for statistical significance.

If the Efficacy-Evaluable Analysis Set (ORR Assessment in Cohort 1) is not equivalent to the Safety Analysis Set for Cohort 1, a sensitivity analysis of ORR will be conducted on the Safety Analysis Set for Cohort 1. The sensitivity analysis will be carried out in the Safety Analysis Set. Patients without postbaseline tumor assessment will be considered as non-responders in the Safety Analysis Set and will be classified as “not assessed.”

Waterfall plots will be provided for the maximum tumor shrinkage from baseline based on the sum of diameters of all target lesions.

Subgroup analyses for ORR will be performed as described in Section [6.4.3](#).

#### PSA Response Rate

PSA response rate is defined as the proportion of patients with a PSA decline  $\geq 50\%$  from baseline confirmed by a second PSA value  $\geq 3$  weeks later. For this primary efficacy endpoint, the PSA assessments will be summarized for the Efficacy-Evaluable Analysis Set (PSA Response Rate Assessment in Cohorts 1 and 2).

PSA response rate (number and proportion of patients) will be presented along with its Clopper-Pearson 2-sided 95% confidence interval. The number and proportion of patients who achieve an unconfirmed PSA decline  $\geq 50\%$  from baseline will also be summarized.

If the primary efficacy endpoint of ORR is statistically significant, PSA response rate will be tested against a historical control PSA response rate, and the null and alternative hypotheses are as follows:

$H_0$ : PSA response rate = 30%

$H_a$ : PSA response rate > 30%

A binomial exact test will be performed for the above hypotheses at a one-sided 0.025 significance level. If the result for PSA response rate is statistically significant, ie, one-sided p-value < 0.025, then PSA response rate will be considered statistically significant. Note that if the primary efficacy endpoint of ORR is not statistically significant, then no claims of statistical significance can be made for the primary efficacy endpoint of PSA response rate.

If the Efficacy-Evaluable Analysis Set (PSA Response Rate Assessment in Cohorts 1 and 2) is not equivalent to the Safety Analysis Set for Cohorts 1 and 2, a sensitivity analysis of PSA response rate will be conducted on the Safety Analysis Set for Cohorts 1 and 2. The sensitivity analysis will be carried out in the Safety Analysis Set. Patients without postbaseline tumor assessment will be considered as non-responders in the Safety Analysis Set and will be classified as “not assessed.”

Subgroup analyses for PSA response rate will be performed as described in Section [6.4.3](#).

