5.6.2. Long-term Follow-up

Patients will be followed for survival and initiation of new anticancer therapy via telephone contact or other means (eg, clinic visit) approximately every 12 weeks ([Appendix 1](#)).

Patients who do not have objective disease progression at the time of pamiparib permanent discontinuation but meet other discontinuation criteria (eg, discontinued for AE and no new anticancer therapy) will continue to have tumor and PSA assessments every 12 weeks and 4 weeks (± 7 days), respectively, until PD or any other reason listed in [Section 5.6.4](#), whichever occurs first. For efficacy assessments as per protocol, refer to [Section 7.3](#) and [Appendix 1](#). If the patient refuses to return for these PSA and tumor assessments or is unable to do so, every effort should be made to contact the patient by telephone to determine the patient's disease status and survival.

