rPFS censoring rule will follow US Food and Drug Administration Guidance for Industry, Clinical Trial Endpoints for Approval of Cancer Drugs and Biologics ([FDA 2007](#)). Data for patients without PD or death at the time of analysis will be censored at the date of the last tumor assessment. Data for patients who initiated new anticancer therapy will be censored at the last tumor assessment date before the introduction of new anticancer therapy. Data for patients who had 2 or more consecutive missed scheduled tumor assessments immediately before PD will be censored at the last tumor assessment date before the 2 missed tumor assessments. Further details will be described in the Statistical Analysis Plan.

OS is defined as the time from the date of the first dose of study drug to death due to any cause.

Time-to-event variables of DOR, duration of PSA response, time to PSA progression, time to SSE, rPFS, and OS will be estimated using the Kaplan-Meier method. The median of these time-to-event variables will be presented along with their 2-sided 95% CI using the Brookmeyer and Crowley method (Brookmeyer and Crowley 1982).

Descriptive statistics will be provided for time to objective response and time to PSA response. Only responders will be included in analyses for DOR, duration of PSA response, time to response, and time to PSA response.

The ORR as assessed by investigator and its exact 2-sided 95% CI will be reported.

[figure not shown]

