The best overall response is the best response recorded from the start of the study drug treatment until the end of treatment taking into account any requirement for confirmation. On occasion a response may not be documented until after the end of therapy so protocols should be clear if post-treatment assessments are to be considered in determination of best overall response. Protocols must specify how any new therapy introduced before progression will affect best response designation. The patient’s best overall response assignment will depend on the findings of both target and nontarget disease and will also take into consideration the appearance of new lesions. Furthermore, depending on the nature of the trial and the protocol requirements, it may also require confirmatory measurement. Specifically, in nonrandomized trials where response is the primary endpoint, confirmation of PR or CR is needed to deem either one the “best overall response”.

The best overall response is determined once all the data for the patient is known. Best response determination in trials where confirmation of CR or PR IS NOT required: Best response in these trials is defined as the best response across all timepoints (for example, a patient who has SD at first assessment, PR at second assessment, and PD on last assessment has a best overall response of PR). When SD is believed to be best response, it must also meet the protocol specified minimum time from baseline. If the minimum time is not met when SD is otherwise the best timepoint response, the patient’s best response depends on the subsequent assessments. For example, a patient who has SD at first assessment, PD at second and does not meet minimum duration for SD, will have a best response of PD. The same patient lost to follow-up after the first SD assessment would be considered unevaluable.

Target Lesions	Nontarget Lesions	New Lesions	Overall Response
CR	CR	No	CR
CR	Non-CR/non-PD	No	PR
CR	Not evaluated	No	PR
PR	Non-PD or not all evaluated	No	PR
SD	Non-PD or not all evaluated	No	SD
Not all evaluated	Non-PD	No	NE
PD	Any	Yes or No	PD
Any	PD	Yes or No	PD
Any	Any	Yes	PD

Abbreviations: CR, complete response; NE, not evaluable; PD, progressive disease; PR, partial response; SD, stable disease.

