#### Duration of PSA Response

Duration of PSA response is defined as the time from the date of the earliest documented PSA response (that is subsequently confirmed) to PSA progression or death due to any cause, whichever occurs first. PSA progression is defined as a  $\geq 25\%$  increase in PSA with an absolute increase of  $\geq 2 \mu\text{g/L}$  above the nadir (or above the baseline for patients with no PSA decline after 12 weeks), confirmed by a second value  $\geq 3$  weeks later. The nadir is defined as the lowest value at or after baseline. For patients who have not died or had a PSA progression event as of the data cutoff date, duration of PSA response will be censored at the date of the last PSA assessment. The PSA assessments will be summarized for patients in the Efficacy-Evaluable Analysis Set

(PSA Response Rate Assessment in Cohorts 1 and 2) who have achieved a confirmed PSA response.

Duration of PSA response will be estimated using the Kaplan-Meier method, and the median duration of PSA response will be presented along with its 2-sided 95% confidence interval using the Brookmeyer and Crowley method. The event-free rate at select timepoints will be calculated along with 2-sided 95% confidence intervals using Greenwood's formula.

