#### Time to PSA Progression

Time to PSA progression is defined as the time from the date of the first dose of study drug to the date of a  $\geq 25\%$  increase in PSA with an absolute increase of  $\geq 2$   $\mu\text{g/L}$  above the nadir (or above the baseline for patients with no PSA decline after 12 weeks), confirmed by a second value  $\geq 3$  weeks later. For patients who have not had a PSA progression event as of the data cutoff date, time to PSA progression will be censored at the date of the last PSA assessment. For this secondary efficacy endpoint, the PSA assessments will be summarized for the Safety Analysis Set (Cohorts 1 and 2).

Time to PSA progression will be estimated using the Kaplan-Meier method, and the median time to PSA progression will be presented along with its 2-sided 95% confidence interval using the Brookmeyer and Crowley method. The event-free rate at select timepoints will be calculated along with 2-sided 95% confidence intervals using Greenwood's formula.

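### PSA response, its duration and time to PSA progression have no cut-off at new anticancer therapy, so a PSA fall on a later drug can be credited to pamiparib

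*SAP*

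**What the plan says.** SAP 6.4.1, under PSA Response Rate, defines a responder as a patient whose PSA falls by at least half from baseline, with a second value at least 3 weeks later in support. It continues "For this primary efficacy endpoint, the PSA assessments will be summarized" and names the evaluable set for Cohorts 1 and 2. Neither this text nor the matching definitions in Protocol 2.2.1 and 10.2.1 close the assessment window or mention new anticancer therapy. The rate is tested against the null "PSA response rate = 30" percent: "A binomial exact test will be performed for the above hypotheses at a one-sided 0.025 significance level".

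SAP 6.4.2 handles patients without an event in the same way for both PSA time-to-event endpoints: "duration of PSA response will be censored at the date of the last PSA assessment" and "time to PSA progression will be censored at the date of the last PSA assessment". The treatment being taken at that last value plays no part.

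The rule for rPFS is different. Protocol 10.2.2 says: "Data for patients who initiated new anticancer therapy will be censored at the last tumor assessment date before the introduction of new anticancer therapy". SAP Table 5, row 5, carries the same rule, and SAP 6.4.2 applies the Table 5 rules to DOR apart from the missing-baseline case.

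On data collection, Protocol 5.6.2 keeps PSA at 4-week intervals for patients who stop pamiparib without objective progression, "until PD or any other reason listed in" Section 5.6.4. On tumor response, the protocol's RECIST text in Appendix 2 says: "Protocols must specify how any new therapy introduced before progression will affect best response designation".

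**The concern.** In a single-arm trial the response rate is read as the drug's own effect. If a PSA value taken on a later drug can satisfy the definition, part of the counted rate may belong to that drug, and the comparison with the 30% historical rate leans towards success. A later drug that lowers PSA would also postpone PSA progression, which lengthens both PSA time-to-event endpoints. The sponsor applies a new-therapy rule to the radiographic endpoints and gives no reason for leaving it off the PSA ones. PSA response is a primary endpoint and also drives the interim futility rule in SAP Section 7.

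**Working it through.** **Step 1. The rules side by side.**

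| Endpoint | Rule at new anticancer therapy | Place |
|---|---|---|
| PSA response | none | SAP 6.4.1 |
| Duration of PSA response | none; censored at last PSA | SAP 6.4.2 |
| Time to PSA progression | none; censored at last PSA | SAP 6.4.2 |
| ORR | none stated | SAP 6.4.1 |
| rPFS | censored | Protocol 10.2.2; SAP Table 5, row 5 |
| DOR | censored, through Table 5 | SAP 6.4.2 |

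**Step 2. Can such a PSA value be recorded?** Protocol 5.5.1 lists starting new anticancer therapy as a reason to stop pamiparib, separate from PD. Protocol 5.6.2 then ends PSA collection at PD or at a reason in Section 5.6.4. That list covers withdrawal of consent, investigator's discretion, loss to follow-up, death, termination by the sponsor, and other reasons at the discretion of the sponsor or a health authority. New therapy is not on it. Appendix 1, footnote k, continues PSA for patients without PD at the End-of-Treatment Visit and makes no exception for new therapy. So the route is open, though narrow. Footnote p shows that new-therapy information is collected in long-term follow-up, so a cut-off can be derived.

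**Step 3. Reproduce the plan's own figure.** Inputs from SAP Section 5 and 6.4.1: n = 80, null 30%, alternative 50%, one-sided 0.025, exact binomial. The critical value is the smallest r with P(X ≥ r | 80, 0.30) < 0.025.

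- r = 32 gives 0.0360, which is too large.
- r = 33 gives 0.0211, so at least 33 responders are needed.
- Power is P(X ≥ 33 | 80, 0.50) = 0.9535. The plan states 95%, so the figure reproduces.

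**Step 4. Illustrate the gap.** Let f be the share of true pamiparib non-responders with PSA recorded on the next drug, and q the share of those with a confirmed 50% fall. Both are assumptions. With a true rate of 30%, the counted rate is p = 0.30 + 0.70 × f × q, and the chance of a positive PSA test is P(X ≥ 33 | 80, p). The expected number of extra responders is 80 × 0.70 × f × q.

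| f | q | Counted rate | Extra responders | Chance of a positive test |
|---|---|---|---|---|
| 0 | – | 30.0% | 0 | 0.021 |
| 5% | 10% | 30.35% | 0.28 | 0.025 |
| 5% | 30% | 31.05% | 0.84 | 0.034 |
| 10% | 20% | 31.4% | 1.12 | 0.040 |
| 10% | 30% | 32.1% | 1.68 | 0.053 |
| 20% | 20% | 32.8% | 2.24 | 0.070 |
| 20% | 30% | 34.2% | 3.36 | 0.114 |

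**Step 5. The same without f and q.** If exactly one next-drug response is always added, 32 true responses suffice and the chance at 30% is 0.036. With two it is 0.059, and with three 0.092.

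**Step 6. The interim rule.** The chance of at least 6 responses in 20 at a true 30% is 0.584. It becomes 0.661 with f = 10% and q = 30%, and 0.730 with f = 20% and q = 30%.

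**The case against.** The strongest point is SAP Section 8. The trial stopped after 13 patients, the interim look was not reached, and no efficacy analysis will be run; PSA data will be listed and discussed. No planned test is distorted. This stands in full and moves the practical remedy to the listings and the report text.

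The route is also narrower than the bare definition suggests. PSA collection ends at PD. The example in Protocol 5.6.2 of a patient who stays in follow-up is one with no new therapy. Protocol 6.2.2 bars other anticancer therapy during the study, and Protocol 5.7 treats long-term follow-up as on study. This stands as a limit on how often the problem could arise. It does not close the gap: the example is not a stopping rule, Protocol 5.5.1 foresees new therapy, and a conduct rule does not say how recorded values are analysed.

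The figures are illustrations. In particular, q would have to apply to patients who did not respond to pamiparib, and their PSA must fall to half of the value before pamiparib (baseline is set by the first dose, SAP 6.2.1). Low values of f and q leave the error at about the nominal level. If both null hypotheses hold, a false PSA claim also needs a false ORR claim, so it cannot be more likely than the size of the ORR test: 0.0132, with at least 14 of 50.

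For ORR, Appendix 2 defines best overall response by default as running to the end of treatment, which would exclude most scans on a later drug. That softens the ORR point, although the same appendix asks for an explicit rule.

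Protocol 7.3.2 refers to Appendix 10 for PSA response. The PSA outcome rows of that appendix are not legible in the text available here, so a window stated there cannot be ruled out. SAP 6.4.1 gives its definition without pointing to it.

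Finally, following PSA through later therapy is a defensible treatment-policy choice for the two secondary endpoints, and censoring at new therapy can be informative. The case for the cut-off is stronger for response than for these.

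**Conclusion.** The gap is real on the text: none of the three PSA endpoints is cut at new anticancer therapy, while rPFS and DOR are. A later drug's PSA fall can count as a pamiparib response if a patient stops without PD, starts that drug and still has PSA recorded.

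The size is unknown. Under the assumed ranges (f 5% to 20%, q 10% to 30%) the chance of a positive PSA test at a true 30% moves from 0.021 to between 0.025 and 0.11. These figures describe the PSA test once the ORR gate is passed.

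Two stronger readings go beyond the documents. A reader might infer that the PSA result is biased upward; the text shows only that it could have been, and Section 8 means no such result will be estimated. A reader might also take the switching share as a fraction of all 80 patients: 20% of them, with 30% responding, gives a counted rate of 0.30 + 0.20 × 0.30 = 36% and an error of 0.194. The arithmetic is right, but nothing in the documents supports that share or that response rate.

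**What to change.** In SAP 6.4.1, count only PSA values, including the confirming one, taken on or before the start of new anticancer therapy. Apply the same cut to tumor assessments for ORR, which also answers the request in Appendix 2.

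In SAP 6.4.2, censor duration of PSA response and time to PSA progression at the last PSA on or before the start of new therapy, to match Table 5, row 5, or report this as a sensitivity analysis. Say what happens to a rise first seen before the switch whose second value comes after it.

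For the report planned under SAP Section 8, flag PSA values taken after the start of new therapy in the listings and do not describe them as pamiparib responses.

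The cost is a few sentences in the SAP and one flag derived from data already collected. The design does not change (at least 33 of 80, power 95.4%). The response rate may be slightly lower.
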